## **Trial Registration**

Clinicaltrials.gov Trial registration identifier: NCT04232358

Ethical Committee of the Capital Region: H-190413740270,

## **Protocol Version and Date**

This document has been written based on information contained in the study protocol version 4, December 2019 approved by the Ethical Committee.

## **Statistical Analysis Plan Version and Date**

Version 1

29th September, 2022

## 2 INTRODUCTION

Achilles tendinopathy (AT) is a frequent and often long-lasting disease especially in athletes. The cumulative incidence in former elite athletes is 50% compared to 5.9% in inactive individuals (Kujala, 2005). In particular, athletes involved in running and jumping activities are at risk (Kvist 1991). In the case of running, the incidence is 9%. In approximately 20% of cases the injury is localized to the tendon enthesis (Lysholm 1987).

In mid-substance AT (in the tendon proximal to tendon attachment), the primary treatment is eccentric exercises that have a positive effect on 60% to 90% of patients (Silbernagel 2001, Maffuli, 2008, 2010, Ohberg). Other studies have shown positive effects of stretching exercises (Porter 2002) and in a randomized study, no difference in outcome could be seen when treating with eccentric exercises compared to stretching exercises (Nørregård 2007). In a recent study at our institute, heavy slow strength training has been shown to be equally effective compared to eccentric training (Beyer 2015). However, patients with AT most distally in the tendon attachment to the bone, called enthesopathy, is often excluded from these studies. Eccentric training in maximum dorsiflexion has been shown to have a poor effect on enthesopathies (Fahlström 2003). In a non-controlled pilot study, a good effect of eccentric exercises avoiding dorsiflexion has been documented in patients with Achilles enthesopathy (Jonsson 2008). In another study, we found that patients with mid-substance AT and patients with Achilles tendon enthesopathy responded equally well to a cautious progressive exercise program (Wetke 2015).

Injection with Cortikosteroid (CS) is often used in the clinic, but since there is usually an absence of inflammatory cells in AT, the rationale behind the treatment is controversial (Khan 2002).

However, a randomized clinical controlled trial (RCT) has shown good efficacy of CS injections given ultrasound-guided in chronic AT (Fredberg 2004). A significant short-term positive effect on symptoms and a reduction in the thickness of the tendons were seen, but relapse of tendinopathy after 6 months, possibly due to an aggressive rehabilitation course. In exercise efficacy studies that include patients with mid-substance AT, 60 to 90% of patients will typically have a positive effect of treatment (Silbernagel 2001, Fahlström 2003, Maffuli 2008). However, the effectiveness of exercise therapy was significantly lower in a mixed cohort that included all consecutive patients with achilles tendinopathy, as well as enthesopathy, where only 26% had a satisfactory effect from

exercise alone (Wetke 2014). Likewise, only 10% of a mixed cohort had satisfactory effect of a program consisting of eccentric exercises for home training (Ram 2013). Overall, exercise most often has a beneficial effect in patients with tendinopathy proximal for attachment, whereas the beneficial effect of training in patients with tendinopathy at the attachment – enthesopathy – is more questionable. In the study by Wetke (2015), it was documented that the exercise therapy by need supplemented with injection of CS mixed with local anesthetics in both mid-substance AT and enthesopathy, but whether this effect was due to a pain-reducing effect of local anesthesia or an anti-inflammatory effect of CS is not known. So far, no RCT study has been conducted assessing the combined effect of exercise and injections in patients with enthesopathy. Our hypothesis is that exercise therapy combined with CS will have a better effect than exercise therapy combined with injection of local anesthetics

The existing standard treatment of AT, without differentiation between tendinopathy in mid-substance or enthesopathy, is, according to clinical guidelines in the Danish Sports Medicine Society (DIMS) and in the Danish Rheumatological Society (DRS), primarily load reduction supplemented by exercise therapy with strengthening exercises. If necessary, this can be supplemented by injection of CS, usually mixed with local anesthetics.

The purpose of our study is to investigate whether the existing standard treatment with load reduction by reduced running and jumping activities and slowly progressed controlled exercises in combination with injection of CS reduces pain and improves function more than treatment consisting of the same load reduction and exercise program combined with placebo injection in patients with enthesopathy.

The study is based on the following hypothesis:

Treatment of Achilles tendon enthesopathy with controlled exercises and reduced running and jumping activities combined with corticosteroid injection (current standard treatment) provides better pain reduction and increase in function than treatment consisting of the same load reduction and exercises combined with placebo injections.

### 3 MATERIAL AND METHODS

Patients with suspected Achilles tendinopathy are usually referred to the Department of Sports Medicine at Bispebjerg Hospital or specialist practice in rheumatology.

#### Inclusion criteria

1. Ultrasound diagnosed Achilles entesopati.
2. In ultrasound scanning, the affected Achilles tendon must be trumpet-shaped thickened in the attachment (enthesis) and with increased flow in the tendon itself.
3. Duration of pain should be a minimum of 3 months
4. Participants are from 18 years to 65 years.
5. Participant may provide relevant and adequate informed consent.

#### Exclusion criteria.

1. Previous lower limb surgery. Arthroscopy of the knee excepted.
2. No known medical conditions, including insulin-dependent diabetes mellitus or rheumatic diseases.
3. Infection of the foot or lower leg.
4. Mental state that does not allow participation.
5. Assessed not able to participate in the exercise therapy.
6. Lack of presence in the region during the project period.
7. Daily use of pain medications, including NSAIDs.
8. Cannot read or understand Danish\*.
9. Steroid injection to treat Achilles enthesopathy/tendinopathy within the last 6 months.
10. Previous allergic reaction to treatment with corticosteroid (Depomedrol®) or local anesthetics.
11. Pregnancy/breastfeeding or planning of pregnancy during the intervention period.

\*Due to the cost of an interpreter, the subject has to read and understand Danish.

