### Randomization method

Randomization must be preceded by informed consent and power of attorney. The randomization of patients is done by an independent project secretary who is not involved in the patient treatment. This is done by a computer randomization program. Patients will be divided equally into 2 groups. The independent project secretary is then in charge of filling out randomization sheets and mixing injection for the investigator. The project secretary must prepare the 2 injections according to the description below, and must keep the randomization sheet for patients secretly and securely locked until the end of the trial, which is defined as 12 months of follow-up of patient number 50. The project secretary will also be responsible for accounting for used medicine. The project secretary has no treatment contact with the patients.

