### **The 2 treatment arms are:**

**GROUP 1** Exercise + placebo injection: Treatment with controlled training controlled via the training app “Injurymap” (CE approved by the Danish Medicines Agency as a medical device) and reduced running and jumping activities combined with injection of local anesthetics. This consists of lidocaine as well as intralipid. Lidocaine is a mild pain reliever and the intralipid is added so that the mixture is not visibly distinguishable from the corticosteroid.

**GROUP 2:** Exercise + corticosteroid injection. Treatment with controlled training controlled via the training app “Injurymap” and reduced running and jumping activities combined with corticosteroid injection. This injection consists of Depo-medrol® (methylprednisolone acetate) 1ml and lidocaine 10mg/ml 1ml.

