### Description of injection of corticosteroid

The corticosteroid injection consists of the mixture of 1 ml of Depomedrol (40 mg/ml) and 1 ml of lidocaine 1% (10mg/ml). The mixtrure will be prepared before injection with the syringe covered with non transparent tape marked with the study number of the patient and stored in a fridge. Under ultrasound guidance, the 2 ml mixture will be injected underneath the tendon close to the enthesis. The preparation of the mixtures will be performed by an assistant not involved in the treatment and without contact to the patients, thereby maintaining the blinding of both the patient and the medical practitioner. Regardless of whether the symptoms are bilateral or unilateral, only one side is injected. As long as there is morning pain above 20 (VAS 0-100) or exercise pain above 20 (VAS 0-100) or overall assessment less than +3 on (Lickert scale from -5 to +5, where "0" is the status at entry and +5 is completely cured), injection is given at inclusion and 1 and 2 months after inclusion, but not more than 3 times.

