### Description of injection of local anesthetics

Local anaesthetic treatment (placebo) will contain a mixture of 1 ml lidocaine 1% (10 mg/ml) and 1 ml 20% Intralipid. Intralipid will be added to give the mixture similar appearance as the corticosteroid injection. The mixture will be prepared before injection with the syringe covered with non transparent tape marked with the study number of the patient and stored in a fridge. The injection technique is the same as for steroid injection. The preparation of the mixtures will be performed by an assistant not involved in the treatment and without contact to the patients, thereby

---

Bispebjerg Hospital      Statistical Analysis Plan  
Exercise/Corticosteroid/placebo in Achilles  
entesopathy

Date: nov 27 2022

maintaining the blinding of both the patient and the medical practitioner. The indication for supplementary injection is similar to injection with corticosteroid.

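### The SAP's allergy exclusion names two of the three injected agents and omits Intralipid, which is half of every placebo injection

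*SAP*

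**What the plan says.** The SAP prints both the allergy rule and the content of both syringes.

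- **Allergy rule** (Exclusion criteria, item 10): "Previous allergic reaction to treatment with corticosteroid (Depomedrol®) or local anesthetics".
- **Steroid syringe**: "The corticosteroid injection consists of the mixture of 1 ml of Depomedrol (40 mg/ml) and 1 ml of lidocaine 1% (10mg/ml" (from the section describing the steroid injection).
- **Placebo syringe** (The 2 treatment arms): "This consists of lidocaine as well as intralipid". The section Description of injection of local anesthetics adds the amounts: it "will contain a mixture of 1 ml lidocaine 1% (10 mg/ml) and 1 ml 20% Intralipid".
- **Number of injections** (Description of injection of corticosteroid): while symptoms stay above the stated thresholds, "injection is given at inclusion and 1 and 2 months after inclusion, but not more than 3 times". For placebo, "The indication for supplementary injection is similar to injection with corticosteroid".
- **Allocation** (Randomization method): "Patients will be divided equally into 2 groups".

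The only other exclusion that might be thought relevant is item 2: "No known medical conditions, including insulin-dependent diabetes mellitus or rheumatic diseases". It names no allergy or drug reaction, and as an exclusion it is worded the wrong way round.

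**The concern.** An allergy exclusion in a two-arm injection trial has to cover everything a patient might receive in either arm, because eligibility is decided before anyone knows the allocation. Item 10 does this for the steroid arm but not for the placebo arm. A candidate who has reacted to Intralipid, and who is asked only about corticosteroids and local anaesthetics, has no reason to mention it.

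Blinding makes the screen more important than usual. Under the SAP's Blinding and Randomization method sections, the injecting doctor sees a taped syringe carrying only a research number, and the secretary who prepares it has no treatment contact with the patient. Whoever knows the content does not treat the patient, and whoever treats the patient does not know the content. Screening before allocation is the only safeguard the SAP describes. What is at stake is the safety of individual participants, not the trial's inference.

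**Working it through.** The SAP gives no figure of its own on this point to reproduce. The check compares the allergy rule with the syringe contents and then counts planned exposure.

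**Coverage of item 10**

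| Syringe | Content | Named in item 10 |
|---|---|---|
| Steroid | 1 ml Depomedrol | yes |
| Steroid | 1 ml lidocaine | yes (local anaesthetic) |
| Placebo | 1 ml lidocaine | yes (local anaesthetic) |
| Placebo | 1 ml 20% Intralipid | no |

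The steroid syringe has 2 of 2 agents covered and the placebo syringe 1 of 2. Counting distinct agents (Depomedrol, lidocaine, Intralipid), 2 of 3 are covered.

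**Other items.** None of the other ten exclusions names Intralipid or an allergic reaction. Item 2 deals with medical conditions.

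**Planned exposure to the unnamed agent**

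- Share of each placebo injection: 1 ml / (1 ml + 1 ml) = 50%.
- Maximum per placebo patient: 3 injections × 1 ml = 3 ml, out of 3 × 2 ml = 6 ml injected.
- Patients exposed: 25 of 50 (Trial Design).
- Maximum number of placebo injections: 25 × 3 = 75.

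The 75 is a ceiling for the 25 planned patients, because the second and third injections depend on persisting symptoms. It does not count replacements: under Trial Design, treated patients who miss the 1-month visit are replaced, so slightly more than 25 people could receive placebo.

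**What cannot be computed.** The SAP gives no proportion of candidates with a known Intralipid reaction and no reaction rate, so no risk figure can be derived.

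**The case against.** The strongest objection is one of scope. Contraindications and screening questions belong to the protocol. This SAP says it was written from protocol version 4, which is not available here and may already exclude Intralipid reactions. That limit stands, and the conclusion is confined to the list printed in the SAP. It does not remove the point, because the SAP does not leave the matter to the protocol: it states an allergy rule, states what is injected, and the first does not cover the second.

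A second objection is that item 2 is a broad catch-all that could take in a known serious drug reaction. It is true that the list overlaps elsewhere (infection and mental state, items 3 and 4, could also fall under item 2), so redundancy with item 10 does not by itself settle how item 2 is to be read. But item 2 names no drug reaction, is worded in reverse, and sits in a list that gives drug allergy its own item. A screener could not be expected to ask about Intralipid on the strength of it.

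A third objection is that no risk has been shown and that nothing in the SAP says Intralipid is allergenic. The first half stands: the counts above measure exposure only. But the sponsor already screens for reactions to the other two injected agents, and the same rule applied consistently would include the third, which is in the syringe only to match appearance and viscosity.

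Finally, a change to the SAP alone does not alter screening. That is correct, and the fix allows for it.

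**Conclusion.** The concern holds as a minor participant-safety gap. As printed, item 10 covers 2 of the 3 injected agents. The omitted one is half of every placebo injection, planned for 25 of 50 patients, at up to 3 ml each and at most 75 injections before replacements. Followed literally, the rule leaves a person with a known Intralipid reaction eligible for randomisation.

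This rests on two readings: that item 2 is not meant to cover drug reactions, and that the SAP's list is the one being judged. If the protocol already names Intralipid, what remains is a correction to the SAP's list. No claim is made about how often such reactions occur. Sample size, power, alpha, estimand and analysis are unaffected.

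**What to change.** Extend item 10, and the question put to candidates before randomisation, to: *previous allergic reaction to corticosteroid (Depomedrol), local anaesthetics, Intralipid, or any component of either study injection*. Check the protocol's list and make the same change there if it has the same gap.

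The cost is one phrase in the eligibility list and in the screening question. A protocol change might need a minor amendment with ethics approval, because recruitment had already started when the SAP was signed (section 4.4). With version 1 dated September 2022 and enrolment scheduled to the end of June 2023, the change could still protect patients yet to be enrolled. The loss of eligible patients should be about one at most; this is a judgement, since the SAP gives no figure.

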## 4 STUDY METHODS

Triple blinded Randomized Controlled Trial.

### Randomization method

Randomization must be preceded by informed consent and power of attorney. The randomization of patients is done by an independent project secretary who is not involved in the patient treatment. This is done by a computer randomization program. Patients will be divided equally into 2 groups. The independent project secretary is then in charge of filling out randomization sheets and mixing injection for the investigator. The project secretary must prepare the 2 injections according to the description below, and must keep the randomization sheet for patients secretly and securely locked until the end of the trial, which is defined as 12 months of follow-up of patient number 50. The project secretary will also be responsible for accounting for used medicine. The project secretary has no treatment contact with the patients.

### Blinding

**Randomization** is performed by an independent office employee not involved in patient care ([name]) using a computer generated randomization schedule (MINIMPY, Maghaei 2010) using permuted block sizes (four to six). The employee is blinded to the block sizes. The allocation of each patient is stored in a computer drive with exclusive access only for the responsible office employee ([name]).

All patients are given consecutive research numbers.

**Patients are blinded** to treatment: The syringe are blinded with tape only showing the patients research number. The content is visually identical and with similar viscosity by mixing intralipid to the placebo injection. There is a risk that blinding will be affected by the known side effects of injection with corticosteroids (flare-up and flushing). Therefore, at the first check-up after the injection, patients are asked which of the two groups they think they have been in.

**Doctors performing the injections are blinded** (JR, CB): The syringe are blinded with tape only showing the patients research number. The content is visually identical and with similar viscosity by mixing intralipid to the placebo injection.

**Data entry investigator are blinded** (JR). All data is transferred from Redcap / CRF to Xcel sheet without knowledge of treatment group allocation. After all data is transferred, the patients are divided into two groups “A” and “B” but still blinded to actual treatment groups, by information from the independent office employe.

**Statistician is blinded** (PSM): After data entry and the patients are divided in two groups: group A and group B still blinded to the actual treatment group, all statistics are performed until agreement of the results. Thereafter the blinding is broken.

### **The 2 treatment arms are:**

**GROUP 1** Exercise + placebo injection: Treatment with controlled training controlled via the training app “Injurymap” (CE approved by the Danish Medicines Agency as a medical device) and reduced running and jumping activities combined with injection of local anesthetics. This consists of lidocaine as well as intralipid. Lidocaine is a mild pain reliever and the intralipid is added so that the mixture is not visibly distinguishable from the corticosteroid.

**GROUP 2:** Exercise + corticosteroid injection. Treatment with controlled training controlled via the training app “Injurymap” and reduced running and jumping activities combined with corticosteroid injection. This injection consists of Depo-medrol® (methylprednisolone acetate) 1ml and lidocaine 10mg/ml 1ml.

### **Description of load reduction**

For the first 3 months, the patient must refrain from jumping and running activities (impact training). They are allowed to do non-impact training such as cycling, swimming, rowing and strength training. Shoes that do not press into the back of the heel are recommended. After 3 months, they must slowly return to their previous sports activity with jumping and running, without provoking further pain or morning stiffness.

### Description of training with CE approved training app: Injurymap.

The strength training will consist of a gently progressive training program with daily training. The training program starts with gentle exercises without dorsal flexion and is slowly progressed after feedback from the patient. If the patient register pain of 5 or above on a 0-10 scale, the program will choose a lighter exercise and not until 2 weeks later offer the same exercise again. The program consists of both movement exercises, stretching exercises, balance exercises and strength exercises similar to the exercise program we have used and found effective in a previous study (Wetke 2015)

For bilateral symptoms, both sides must be trained, but only one side is included in the evaluation of outcome parameters.

### Description of injection of corticosteroid

The corticosteroid injection consists of the mixture of 1 ml of Depomedrol (40 mg/ml) and 1 ml of lidocaine 1% (10mg/ml). The mixtrure will be prepared before injection with the syringe covered with non transparent tape marked with the study number of the patient and stored in a fridge. Under ultrasound guidance, the 2 ml mixture will be injected underneath the tendon close to the enthesis. The preparation of the mixtures will be performed by an assistant not involved in the treatment and without contact to the patients, thereby maintaining the blinding of both the patient and the medical practitioner. Regardless of whether the symptoms are bilateral or unilateral, only one side is injected. As long as there is morning pain above 20 (VAS 0-100) or exercise pain above 20 (VAS 0-100) or overall assessment less than +3 on (Lickert scale from -5 to +5, where "0" is the status at entry and +5 is completely cured), injection is given at inclusion and 1 and 2 months after inclusion, but not more than 3 times.

### Description of injection of local anesthetics

Local anaesthetic treatment (placebo) will contain a mixture of 1 ml lidocaine 1% (10 mg/ml) and 1 ml 20% Intralipid. Intralipid will be added to give the mixture similar appearance as the corticosteroid injection. The mixture will be prepared before injection with the syringe covered with non transparent tape marked with the study number of the patient and stored in a fridge. The injection technique is the same as for steroid injection. The preparation of the mixtures will be performed by an assistant not involved in the treatment and without contact to the patients, thereby

---

Bispebjerg Hospital      Statistical Analysis Plan  
Exercise/Corticosteroid/placebo in Achilles  
entesopathy

Date: nov 27 2022

maintaining the blinding of both the patient and the medical practitioner. The indication for supplementary injection is similar to injection with corticosteroid.

